3.5.3 Immunogenicity Assessments

Blood samples for the following immunogenicity assessments will be collected at the time points indicated in the Schedule of Events (Table 5):

- Serum neutralizing antibodies (nAb) against ZIKV
- Serum binding antibodies (bAb) against ZIKV

Sample aliquots will be designed to ensure that backup samples are available and that adequate vial volumes may allow further testing needs. The actual time and date of each sample collected will be recorded in the eCRF, and unique sample identification will be utilized to maintain the blind at the laboratory at all times and to allow for automated sample tracking and housing. Handling and preparation of the samples for analysis, as well as shipping and storage requirements, will be provided in a separate laboratory manual.

3.5.4 Total Blood Volume

The approximate blood volumes to be collected from each participant during the study are provided in Table 4.

Table 4: Total Blood Volume

Assessment	Blood Volume per Sample	Scheduled Number of Collections ^a	Total Amount of Scheduled Blood
Clinical Laboratory Assessments			
Hematology	2 mL	6	12 mL
Serum chemistry	6.5 mL	6	39 mL
Coagulation	3 mL	6	18 mL
Flavivirus screening by ELISA ^b	12 - 16 mL	1	12 - 16 mL
Serology ^c	6 mL	1	6 mL
Immunogenicity Assessments			
Serum neutralizing antibodies against Zika by neutralization assays	8 mL	5	40 mL
Serum binding antibodies against Zika by ELISA	4 mL	5	20 mL
IgG and IgM antibodies against envelope- and NS1-based antigens by ELISA	4 mL	5	20 mL
Participant Total	167 - 171 mL		

Abbreviations: IgG = immunoglobulin G; IgM = immunoglobulin M; ELISA = enzyme-linked immunosorbent assay; HIV = human immunodeficiency virus; NSI = nonstructural protein 1.

- ^a Additional blood collections may be required at the discretion of the investigator to follow up on abnormal results.
- b Flavivirus testing by ELISA will include testing for dengue, West Nile, and Zika.
- Serology testing will include hepatitis B surface antigen, hepatitis C virus antibody, HIV virus type 1 and 2, Separate counseling and consent will be provided for HIV testing.

3.5.5 Safety Assessments

Safety assessments will include monitoring and recording of solicited AEs (local and systemic reactogenicity events) and unsolicited AEs, SAEs, AESI, AEs leading to study withdrawal, and MAAEs; clinical laboratory test results (hematology, serum chemistry, and coagulation); vital sign measurements; and physical examination findings. If an MAAE occurs that evokes clinical symptomatology consistent with a flavivirus infection, serology and polymerase chain reaction testing against dengue will be uniformly collected.

3.5.6 Solicited Safety Measurements

The term "reactogenicity" refers to selected signs and symptoms (AEs) occurring after vaccine administration that the participants are systemically asked to record. Participants will record such occurrences in a diary card (Section 3.5.2) on the day of each vaccine administration and for the 6 days after vaccine administration. Participants will be instructed to call or return to the clinic within 24 hours if a reactogenicity score reaches Grade 3 or greater during the first 6 days after vaccination.

The following AEs are included on the diary card:

- Solicited local AEs:
 - Injection site pain
 - Injection site erythema
 - Injection site induration/swelling
- Solicited systemic AEs:
 - Body temperature (oral)
 - Generalized myalgia (muscle ache or pain)
 - Generalized arthralgia (joint ache or pain)
 - Headache
 - Fatigue/malaise (unusual tiredness)
 - Nausea/vomiting
 - Chills
 - Rash

Appropriate reactogenicity measurements will be taken using the tools provided by Sponsor (oral thermometer and measuring device; Section 3.5.2). The investigator will later review, confirm, and grade reactogenicity according to the Guidance for Industry: Toxicity grading scale for healthy adult and adolescent volunteers enrolled in preventative vaccine clinical trials (DHHS 2007; Table 6).

In case of any rash episode observed within 6 days after study vaccination, the participants will be instructed to contact the study site within 24 hours. During subject evaluation, the investigator should categorize the rash as one of the following:

- Rash no longer present and history not consistent with urticaria.
- Rash no longer present but history is consistent with urticaria.
- Rash present but clinical findings are not consistent with urticaria. Alternative diagnosis should be specified as an AE.
- Rash present and clinical findings consistent with urticaria.

If a solicited local or systemic reactogenicity AE continues beyond 7 days after vaccine administration, it will also be recorded as an AE in the eCRF from 8 days after vaccination until the AE has resolved or stabilized (Section 3.5.7.1.1).

Other solicited reactions will include the following:

- Use of analgesics and/or antipyretics will be recorded as absent or present, and participant will indicate if use was for treatment or prophylaxis.
- To improve recall before the next visit, participants will record the incidence of unsolicited AEs and any medication (prescription and over the counter [excluding vitamins and minerals]) using the diary card during the 28 days after each vaccine administration.

All AEs necessitating an unscheduled physician visit or medical attention or leading to withdrawal from the study will also be collected throughout the study, as detailed in Section 3.5.7.

3.5.7 Unsolicited Safety Measurements

3.5.7.1 Adverse Events

The investigator is responsible for reporting all AEs that are observed or reported during the study, regardless of their relationship to vaccine or their clinical significance. If there is any doubt as to whether a clinical observation is an AE, the event should be reported.

3.5.7.1.1 Definitions

An AE is defined as any untoward medical occurrence associated with the use of a drug in humans, whether or not considered drug related. Participants will be instructed to record any AEs (solicited or unsolicited) in the diary card.

A treatment-emergent AE (TEAE) is defined as any event not present before exposure to vaccine or any event already present that worsens in intensity or frequency after exposure.

A suspected adverse reaction is any AE for which there is a reasonable possibility that the vaccine caused the AE. For the purposes of investigational new drug safety reporting, "reasonable possibility" means that there is evidence to suggest a causal relationship between the vaccine and the AE. A suspected adverse reaction implies a lesser degree of certainty about causality than adverse reaction, which means any AE caused by a vaccine. Adverse reactions are a subset of all suspected adverse reactions for which there are reasons to conclude that the drug caused the event.

An unsolicited AE is any AE reported by the participant that is either (1) not specified as a solicited AE in the protocol or (2) specified as a solicited AE in the protocol, but its onset occurs outside of the protocol-defined post-vaccination period for reporting solicited AEs (i.e., for the 7 days after each vaccination; Section 3.5.6 for additional information on solicited safety measures).

An AE or suspected adverse reaction is considered "unexpected" if it is not listed in the IB or is not listed at the specificity or severity that has been observed with the vaccine being tested or, if an IB is not required or available, it is not consistent with the risk information described in the general investigational plan or elsewhere in the current application. For example, under this definition, hepatic necrosis would be unexpected (by virtue of greater severity) if the IB referred only to elevated hepatic enzymes or hepatitis. Similarly, cerebral thromboembolism and cerebral vasculitis would be unexpected (by virtue of greater specificity) if the IB listed only cerebral vascular accidents. "Unexpected," as used in this definition, also refers to AEs or suspected adverse reactions that are mentioned in the IB as occurring with a class of drugs or as anticipated from the pharmacological properties of the drug but are not specifically mentioned as occurring with the particular drug under investigation.

Unsolicited AEs will also be evaluated by the investigator for the coexistence of any of the other following conditions:

• Medically attended AE, defined as an AE that leads to an unscheduled visit to a healthcare practitioner

Any solicited AE (Section 3.5.6) that meets any of the following criteria must be entered as an AE in the eCRF:

- Solicited local or systemic AE leading to the participant withdrawing from the study or the participant being withdrawn from the study by the investigator
- Solicited local or systemic AE lasting beyond 7 days post-vaccination
- Solicited local or systemic AE that leads to participant withdrawal from vaccine
- Solicited local or systemic AE that otherwise meets the definition of an SAE
- Laboratory test result or vital sign measurements with a toxicity score of Grade 3 or greater

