3.6 Statistical Analysis Plans

3.6.1 Primary Endpoints

The following are the primary endpoints of the study:

• Frequency and grade of each solicited local and systemic reactogenicity AE during a 7-day follow-up period after each vaccination

- Frequency and grade of any unsolicited AEs during the 28-day follow-up period after each vaccination
- Frequency of any MAAE, SAE, and AESI from Day 1 to the EOS Visit at Month 13

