7.6.1 Solicited Adverse Reactions

The term "reactogenicity" refers to selected signs and symptoms (ARs) occurring after vaccine administration that the participants are systematically asked to record. Participants will record such occurrences in a diary card on the day of each vaccine administration and for the 6 days after vaccine administration.

Date Issued: 25May2021

The local solicited ARs include injection site pain, injection site erythema, and injection site induration/swelling.

The systemic solicited ARs include fever, generalized myalgia (muscle ache or pain), generalized arthralgia (joint ache or pain), headache, fatigue/malaise (unusual tiredness), nausea/vomiting, chills, and rash.

For erythema, swelling, and fever, grade will be derived based on the measurement recorded on the diary card as noted in Table 2. Other events will be assessed for grade by the investigator based on the Toxicity Grading Scale for Healthy Adult and Adolescent Volunteers Enrolled in Preventative Vaccine Clinical Trials [DHHS 2007] and recorded in the eCRF.

Table 2: Toxicity Grads for Erythema, Swelling, and Fever

| | Grade 1 | Grade 2 | Grade 3 | Grade 4 |
|----------|---------------|---------------|---------------|----------|
| Erythema | 21 - 50 mm | 51 – 100 mm | > 100 mm | |
| Swelling | 21 – 50 mm | 51 – 100 mm | > 100 mm | |
| Fever | 38.0 – 38.4°C | 38.5 – 38.9°C | 39.0 – 40.0°C | > 40.0°C |

Any solicited AR that meets any of the following criteria will be entered as an AE in the eCRF:

- Solicited local or systemic AR leading to the participant withdrawing from the study or the participant being withdrawn from the study by the investigator
- Solicited local or systemic AR lasting beyond 7 days post vaccination
- Solicited local or systemic AR that leads to participant withdrawal from vaccine
- Solicited local or systemic AR that otherwise meets the definition of an SAE
- Laboratory test result or vital sign measurements with a toxicity score of Grade 3 or greater or that is deemed clinically significant by the investigator for any grade

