7.6.2 Adverse Events

An unsolicited AE is any AE reported by the participant that is either (1) not specified as a solicited AE in the protocol or (2) specified as a solicited AR in the protocol, but its onset occurs outside of the protocol-defined post vaccination period for reporting solicited AEs (ie, for the 7 days after each vaccination). A solicited ARs that meet the criteria for an SAE will also be recorded as an unsolicited AE.

A treatment-emergent AE (TEAE) is defined as any AE not present before exposure to vaccine or any AE already present that worsens in intensity or frequency after exposure. Only TEAEs are collected in this study.

An MAAE is defined as an AE that leads to an unscheduled visit to a healthcare practitioner.

Unsolicited AEs will be coded by PT and SOC using MedDRA and summarized by treatment, vaccination (first or second) and overall. Summaries for each vaccination will include AEs that occur during the 28 -day follow-up period after each vaccine.

All summaries of unsolicited AEs will present number and percentage of subjects in each category. For those summaries presented by PT, the preferred terms will be sorted in descending order of frequency within the mRNA-1893 treatment group.

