7.6.2.1 Overview of Adverse Events

An overall summary of unsolicited TEAEs including the number and percentage of participants who experience the following will be presented:

- All unsolicited TEAEs
- All unsolicited serious TEAEs
- All unsolicited TEAEs leading to death

- All unsolicited TEAEs leading to vaccination discontinuation
- All unsolicited TEAEs of grade 3 or 4
- All unsolicited TEAEs of special interest
- All unsolicited medically-attended TEAEs

The table will also include number and percentage of participants with unsolicited, treatment-related TEAEs in each of the above categories.

The overall summary will also be summarized separately for flavivirus seropositive and seronegative participants.

In addition, listings containing individual participant data for TEAEs, TEAEs leading to vaccination discontinuation, SAEs, AESIs, and medically-attended TEAEs will be provided separately.

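### The primary endpoint is any MAAE, but the only planned count covers unsolicited events, so a brief, non-serious solicited reaction that prompts a doctor or ER visit has no explicit route into it.

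*Protocol*

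**What the plan says.** **Endpoint and definition (broad).** Protocol 3.6.1 lists as primary "Frequency of any MAAE, SAE, and AESI from Day 1 to the EOS Visit at Month 13", and SAP 4.1 repeats it. Protocol 3.5.7.1.1 gives the definition: "Medically attended AE, defined as an AE that leads to an unscheduled visit to a healthcare practitioner". SAP 7.6.2 defines the term in the same way. Neither limits it to unsolicited events.

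**Collection (broad).** Protocol 3.5.6, the section on solicited events, says that "All AEs necessitating an unscheduled physician visit or medical attention" will be collected throughout the study, and refers to Section 3.5.7 for the detail. Protocol 3.5.7.2 has MAAEs assessed from Day 1 through Month 13. Footnote n of the Schedule of Events (Table 5) requires all of them to be reported within 24 hours.

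**Assessment, data entry and counting (narrow).**
- Protocol 3.5.7.1.1 introduces medical attendance with "Unsolicited AEs will also be evaluated by the investigator for the coexistence of any of the other following conditions".
- The same section continues: "Any solicited AE (Section 3.5.6) that meets any of the following criteria must be entered as an AE in the eCRF". Its criteria are study withdrawal, persistence beyond 7 days, withdrawal from vaccine, seriousness, and a laboratory or vital-sign result of Grade 3 or higher.
- SAP 7.6.1 has the parallel list ("Any solicited AR that meets any of the following criteria will be entered as an AE"). It widens the laboratory and vital-sign item and still omits medical attendance.
- SAP 7.6.2 adds that solicited "ARs that meet the criteria for an SAE will also be recorded as an unsolicited AE". It has no matching sentence for medically attended reactions.
- SAP 7.6.2.1 supplies the only MAAE row in the planned tables: "All unsolicited medically-attended TEAEs".

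**The concern.** The endpoint covers any MAAE, while the instructions that produce the number cover unsolicited ones. During the week after each dose, reactions on the solicited list are by definition not unsolicited. If one of them sends a participant to a practitioner or an ER, it meets the MAAE definition, yet the plan does not say how it gets into the MAAE table.

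At stake is whether the reported MAAE frequency measures what the protocol calls a primary endpoint. Such visits are foreseeable: protocol 3.5 expects reactogenicity to prompt some unscheduled visits, and Table 6 makes an ER visit itself a Grade 4 criterion for pain, headache, fatigue, myalgia and arthralgia.

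**Working it through.** **1. Follow one hypothetical event through the plan.** A headache starts the day after vaccination, is seen in an ER without admission, and is gone by the third day after dosing. It is written on the diary card.

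| Step | Source | Result |
|---|---|---|
| Meets the MAAE definition? | Protocol 3.5.7.1.1; SAP 7.6.2 | Yes |
| Unsolicited? | Same sections | No: solicited term, onset inside the solicited period |
| Grade | Protocol Table 6 | 4, because of the ER visit |
| Serious? | Protocol 3.5.7.1.2 | Not necessarily: no admission, and life-threatening requires immediate risk of death |
| Meets an AE-entry criterion? | Protocol 3.5.7.1.1; SAP 7.6.1 | No: short, no withdrawal, not serious, no qualifying laboratory or vital-sign result |
| Re-entered as a newly reported verbal event? | Protocol 3.5.2 | No: already on the diary card |
| In the MAAE row? | SAP 7.6.2.1 | No: row limited to unsolicited TEAEs |
| In the solicited table? | SAP 7.6.1 | Yes under any grade; the grades named are 1, 2 and 3 |

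**2. Does a precedence rule or a declared change settle it?** SAP Section 2 says the SAP prevails where its methods differ from the protocol, so the narrow row governs. SAP Section 8 declares two changes (the All Enrolled definition, and not computing the differences in AE proportions). Restricting MAAEs to unsolicited events is not one of them.

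**3. The plan's own figure.** Protocol 3.6.4 and SAP 5.2 give the probability of seeing at least one participant with an AE among 24 vaccinated, which is 1 − (1 − p)^24.
- p = 10%: 1 − 0.90^24 = 0.9202 (stated 92%).
- p = 5%: 1 − 0.95^24 = 0.7080 (stated 70.8%).

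Both reproduce. The point disputes no stated figure.

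**4. Size per omitted participant.** Each dose group has 24 vaccinated, and pooled placebo has 4 × 6 = 24. One participant whose only MAAE is omitted changes the group rate by 1/24 = 4.2 percentage points; two change it by 2/24 = 8.3 points.

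**5. How likely is at least one such case?** The documents give no rate, so q, the proportion of vaccinees with a reaction of the step 1 kind, is an assumption. The formula is 1 − (1 − q)^n, with n = 24 for one dose group and n = 4 × 24 = 96 for all vaccinated.

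| Assumed q | One dose group (24) | All vaccinated (96) |
|---|---|---|
| 1% | 21.4% | 61.9% |
| 2% | 38.4% | 85.6% |
| 5% | 70.8% | 99.3% |

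**6. Effect on detection.** Suppose the true MAAE incidence is P and a share s of participants with an MAAE has only omitted events. The chance of counting at least one in 24 is 1 − (1 − P(1 − s))^24.

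| P | s = 0 | s = 25% | s = 50% |
|---|---|---|---|
| 10% | 92.0% | 84.6% | 70.8% |
| 5% | 70.8% | 60.0% | 45.5% |

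Steps 5 and 6 illustrate a range and are not estimates.

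**The case against.** The strongest reply is that the protocol plainly intends to capture these events. Sections 3.5.6 and 3.5.7.2 and footnote n of Table 5 cover MAAEs without restriction. Table 5 records MAAEs in a row separate from unsolicited AEs, safety calls ask about them (3.5.1), and 3.5.7.1 tells the investigator to report when in doubt. The entry list says what must be entered, not that nothing else may be. The SAP's MAAE listing does not carry the word unsolicited. Reporting solicited reactions only in their own tables could also be a deliberate way to avoid showing one event twice.

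Much of this stands as evidence of intent. It does not change the row the SAP tabulates, and a deliberate separation would belong in SAP Section 8.

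Two stronger readings are tempting.

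- **That all 11 solicited terms (3 local + 8 systemic) drop out of the endpoint.** The documents do not support this. Serious, prolonged or withdrawal-causing reactions reach the AE form, as do those newly reported verbally at a visit (protocol 3.5.2). Nor are the remaining events invisible. They count under any grade in the solicited tables and are listed (SAP 7.6.1), and reactogenicity is itself a primary endpoint. A Grade 4 event not reasonably attributable to another cause also meets pause rule 2 (protocol Table 2).
- **That MAAE rates are biased towards placebo and the dose gradient is flattened.** No rate of medically attended solicited reactions is given. The rat study in protocol 1.2 showed dose-dependent injection-site signs, so the direction is plausible, but for this trial it remains inference.

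**Conclusion.** The endpoint and its counting rule do not match. Followed as written, the plan can undercount a primary endpoint by leaving out a limited subset: solicited reactions that are short-lived, non-serious, without withdrawal, documented only on the diary card, and medically attended. Each such participant with no other MAAE costs 4.2 percentage points in a 24-person group. The number affected is unknown, and no effect on the dose comparison is shown.

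The conclusion assumes that the MAAE table is built from the SAP row as worded and that sites use the entry lists as their working rule. If sites already enter these reactions as AEs and the programmers count them, the numerical effect disappears and only the wording needs correcting. The correction should be made because the endpoint is primary and the change is cheap.

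**What to change.** 1. Add one criterion to the entry lists in protocol 3.5.7.1.1 and SAP 7.6.1: a solicited local or systemic reaction that prompts an unscheduled practitioner visit, ER included.
2. In SAP 7.6.2.1, count MAAEs over all AEs, with the solicited part as a sub-row, so that events also shown in the solicited tables are visible and not mistaken for additional ones. If the exclusion is intended, declare it in SAP Section 8 and report medically attended solicited reactions separately.
3. Name Grade 4 explicitly in the SAP 7.6.1 solicited tabulation. Protocol Table 6 defines Grade 4 for most solicited terms and SAP Table 2 defines it for fever. The present wording may allow such a row but does not name it.

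The cost is one line in each document, two table rows and a small query on higher-grade solicited reactions to establish whether care was sought. Reported MAAE rates may rise slightly.

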3.5.7.1.2 Serious Adverse Events

An AE or suspected adverse reaction is considered "serious" (SAE) if, in the view of either the investigator or Sponsor, it results in any of the following outcomes:

- Death
- Is life-threatening
- Inpatient hospitalization or prolongation of existing hospitalization
- Persistent or significant incapacity or substantial disruption of the ability to conduct normal life functions
- Congenital anomaly or birth defect

Important medical events that may not result in death, be life-threatening, or require hospitalization may be considered serious when, based upon appropriate medical judgment, they may jeopardize the participant and may require medical or surgical intervention to prevent one of the outcomes listed in this definition. Examples of such medical events

include allergic bronchospasm requiring intensive treatment in an emergency room or at home, blood dyscrasias or convulsions that do not result in inpatient hospitalization, or the development of drug dependency or drug abuse.

An AE or suspected adverse reaction is considered "life-threatening" if, in the view of either the investigator or Sponsor, its occurrence places the participant at immediate risk of death. It does not include an AE or suspected adverse reaction that, had it occurred in a more severe form, might have caused death. The reporting requirements for SAEs are discussed in Section 3.5.7.3.

